Throughout	Protocol Title Previously read: An Open Label, Multiple-Dose Study to Assess the Safety and Tolerability of GRF6019 Infusions in Subjects with Mild to Moderate Alzheimer’s Disease (AD) Now reads: A Prospective, Randomized, Double-Blind, Dose-Comparison Concurrent Control Study to Assess the Safety and Tolerability of GRF6019 Infusions in Subjects with Mild to Moderate Alzheimer’s Disease (AD)	Updated study design pursuant to direction from the agency
Throughout	Update of study design description from an open label multiple dose study to a prospective, randomized, double-blind dose comparison concurrent control study	Updated study design pursuant to direction from the agency
Throughout	Protocol Version Previously read: v1.0_02AUG2017 Now reads: v2.0_09NOV2017	Version Control
Throughout	Grammar and style changes	For protocol clarity and standardization
Throughout	Update duration of treatment to be approximately 6 months, and total duration in the study to be approximately 7 months.	Improved protocol clarity
Page 8	Measures added to ensure adequate allocation concealment. Added List of Definitions for Infusion Nurse, Infusion Period and Outcomes Assessor	For clarity of updated study design pursuant to direction from the agency

Location	Description	Purpose
Protocol Summary/Precis	Measures added to ensure adequate allocation concealment. Paragraph 3 added to summarize the infusion process and methods for blinding during infusion.	Updated study design pursuant to direction from the agency
2.2 Rationale, Paragraph 8	
Previously read: An open-label, two-arm study design has been selected to identify a safe and feasible dosing paradigm, trends in changes of neurocognitive endpoints, and potential plasma derived factors that may affect these parameters.
 
Now reads: A prospective, randomized, double-blind, dose-comparison concurrent control study design has been selected to reduce or eliminate bias while facilitating the identification of a safe and feasible dosing paradigm, trends in changes of neurocognitive endpoints, and potential plasma derived factors that may affect these parameters.
	Updated study design pursuant to direction from the agency
2.2 Rationale, Paragraph 9	
Previously read: ... the results (of this trial) are nevertheless expected to lay the foundation for larger trials exploring the potential benefit of GRF6019 in AD and other neurodegenerative disorders typified by cognitive dysfunction.
 
Now reads: ... the results (of this trial) are nevertheless expected to lay the foundation for larger trials designed and powered to characterize the potential benefits of GRF6019 in AD and other neurodegenerative disorders typified by cognitive dysfunction.
	Clarification of purpose of study design pursuant to direction of the agency
3. Objectives and Purpose	
Previously read: As an exploratory objective, serial compositional analysis of subject plasma will be performed to identify specific biomarkers...
 
Now reads: As an exploratory objective, blood and plasma will be collected and analyzed to identify specific biomarkers...
	Improved protocol clarity
4.2.2 Secondary Endpoints, Paragraph 1	Confirmation that “This study is neither designed nor powered to detect statistically significant differences in cognitive and motor outcomes...”	Clarification of purpose of study design pursuant to direction of the agency
4.2.2 Secondary Endpoints	Addition of secondary feasibility endpoint related to success of blinding	Updated study design pursuant to direction from the agency
4.2.3 Exploratory Endpoints	Previously read: Cellular samples will be recovered from subject’s plasma to explore epigenetic changes.	Improved protocol clarity

Location	Description	Purpose
	
Now reads: DNA will be extracted from blood samples to explore epigenetic changes.
	
5.3 Strategies for Recruitment and Retention, Paragraph 4	
Clarification that if a trial partner does not reside within a reasonable distance from the inpatient facility, they will be given the option to stay with the subjects or to stay in a nearby hotel/motel.
	Improved protocol clarity
5.4.2 Handling of Participant Withdrawals or Termination	
Addition that subjects who discontinue or are unblinded prior to Visit 8 may be replaced.
	Updated study design pursuant to direction from the agency
6.1.3 Product Storage and Stability	
Previously read: Partially used vials must be discarded. Vials which are cracked or have been previously entered or damaged should not be used, as this may have allowed the entry of microorganisms.
 
Now reads: Vials which are cracked or have been previously entered or damaged should not be used, as this may have allowed the entry of microorganisms.
	Correction to enable drug accountability
6.1.4 Preparation	
Added: IV tubing should be vented. [REDACTED]
	Clarification
6.1.5 Dosing Administration	
Measures added to ensure adequate allocation concealment. Section updated to include provisions for the management and maintenance of study blinding during dosing, including the use of unblinded Infusion Nurses and blinded Outcomes Assessors.
 
Administration Guidelines changed from Appendix 9 to a stand-alone manual.
	Updated study design pursuant to direction from the agency
6.2 Study Agent Accountability	
Measures added to ensure adequate allocation concealment. Addition and explanation of the role of unblinded study staff (study pharmacist, Infusion Nurse, CRA) in accountability of the study agent.
	Updated study design pursuant to direction from the agency
7.1.1.2.3 Vital Signs	
Previously read: Vital signs will be collected at every visit and at multiple time points during the infusion (Appendix 9).
 
Now reads: Vital Signs will be collected at every visit. During infusions, vital signs will be collected within an hour of infusion start, every 15 minutes during the ~2.5 hour infusion period, and at 3 and 6 hours following conclusion of the infusion period.
	Updated for clarity of study procedures. Updated for study design pursuant to direction from the agency

Location	Description	Purpose
	Vital signs will be collected by the blinded Outcomes Assessor.	
7.1.1.3.1 Savonix Neurocognitive Assessments	Clarification that administration of the test should begin no later than one hour after starting the infusion.	Improved protocol clarity
7.2.2.2 PET; 7.3.1 Screening, Visit 1	Section updated to remove use of specific radioligand (Florbetapir) for PET testing. Any radioligand will be accepted for this optional procedure.	Parameters eased for this non-critical test
7.2.2.4 Proteomic and Genetic Biobanking, Paragraph 1	Previously read: Plasma and cellular samples will be collected... Now reads: Blood and plasma will be collected...	Improved protocol clarity
7.2.2.4 Proteomic and Genetic Biobanking, Paragraph 2	Previously read: Cellular samples derived from plasma will be retained... Now reads: Blood samples will be retained...	Improved protocol clarity
7.2.2.4 Proteomic and Genetic Biobanking, Paragraph 2	Added: For information regarding future use of stored samples, see Section 12.5 Future Use of Stored Specimens.	Updated pursuant to direction from the agency
8. Assessment of Safety	Added: Assessment of safety will be conducted by blinded study personnel except in extraordinary circumstances where knowledge of the dose received by a subject is essential. Any instances of unblinding will be managed as indicated in Section 10.6.3.	Updated study design pursuant to direction from the agency
8.4.3 Adverse Events of Special Interest	Previously read: 
 Adverse Events related to increased blood volume Now reads: The following will be considered adverse events of special interest: 
 AEs related to increased blood volume or shifts of fluid between the intravascular and extravascular space Suspected transmission of blood-borne infectious agents 	Expanded AESI
8.5 Study Halting Rules, Safety Eval. Meeting	Amended outcomes from Safety Evaluation Meeting to align with blinded study design. Measures added to ensure adequate allocation concealment.	Updated study design pursuant to direction from the agency
8.6 Safety Oversight	Updated Safety Oversight section and role of Safety Evaluation Meetings for blinded study design	Updated study design pursuant to direction from the

Location	Description	Purpose
		agency
10.1 Statistical and Analytical Plans	Added: The finalization of the SAP will occur prior to clinical database lock and unblinding of the study data.	Updated study design pursuant to direction from the agency
10.2 Statistical Hypothesis	Within-subject changes from baseline for each dosing group and among-group differences will (changed from “may”) be evaluated.	Updated study design pursuant to direction from the agency
10.4.1 General Approach	Further details on the analysis of the primary and secondary endpoints have been clarified. Increased robustness of general statistical approach regarding primary and secondary analysis of endpoints that are continuous as well as categorical. Update to include subjects randomized as part of the disposition summary.	Updated study design pursuant to direction from the agency
10.4.3 Analysis of Secondary Endpoint(s)	Previously read: Among-group differences may be assessed by One-way Analysis of Variance or its nonparametric equivalent Kruskal-Wallis test. Now reads: Among-group differences may be assessed by One-way Analysis of Covariance (ANCOVA) or its nonparametric equivalent test.	Improved protocol clarity
10.4.7 Planned Interim Analyses	Added: If such an ad hoc safety interim analysis is conducted, the treatment assignment will remain masked.	Updated study design pursuant to direction from the agency
10.5 Sample Size	Updated to reflect target of 40 subjects randomized (vs. enrolled)	Updated study design pursuant to direction from the agency
10.6.1 Enrollment/ Randomization/ Masking Procedures	Section updated to address design deficiencies and measures to minimize bias are elucidated. The trial continues to be randomized and is now designed to be blinded to the study subjects, sponsor, investigators, medical providers, and outcome assessors. The details of the enrollment, randomization and masking procedures to minimize bias are detailed in this section, including labs.	Updated study design pursuant to direction from the agency
10.6.2 Evaluation of Success of Blinding	Section added.	Updated study design pursuant to direction from the agency
10.6.3 Breaking the Study Blind/ Participant Code	Section added.	Updated study design pursuant to direction from the agency
12.5 Future Use of Stored Specimens	Amended to address potential privacy issues subjects need to be aware of at time of informed consent regarding future use of retained samples, including how confidentiality will be maintained, how long samples will be held by Alkahest,	Updated pursuant to direction from the agency

Location	Description	Purpose
	how they will be used, and what happens if Alkahest transfers ownership to another commercial sponsor.	
19. Revision History	Addition of revision history table for Protocol Version 2.0 dated 09NOV2017	Version control

SAE	serious adverse event
SAF	Safety Population
SAP	Statistical Analysis Plan
SD	standard deviation
SOB	Sum of Boxes
TEAE	Treatment-emergent AE
TFLs	Tables, Figures, and Listings

vMRI	Volumetric Magnetic Resonance Imaging
WHO	World Health Organization

1 INTRODUCTION

This statistical analysis plan (SAP) describes the planned statistical analyses for the study entitled “A Prospective, Randomized, Double-Blind, Dose-Comparison Concurrent Control Study to Assess the Safety and Tolerability of GRF6019 Infusions in Subjects with Mild to Moderate Alzheimer’s Disease” (V6.0 12OCT2018, V7.0 02NOV2018). Analysis related to exploratory objectives (assessment of changes in composition and distribution of blood-based and CSF (in consenting subjects) biomarkers, as well as changes in imaging results as measured by vMRI, fMRI, and ASL) will be described in a separate plan. Mock shells for the CSR Appendix 14 are also produced as a separate working document to facilitate programming of Tables, Figures, and Listings (TFLs) according to the finalized SAP. The SAP is to be interpreted in conjunction with the protocol. If the final clinical study report contains changes to any planned statistical analyses, the justification for any such differences will be fully documented in the CSR.

1.1 Study Objectives

Primary Objective

To assess the safety, tolerability and feasibility of GRF6019, a [REDACTED] human plasma protein fraction administered by IV infusion in subjects with mild to moderate Alzheimer’s Disease (AD).

Secondary Objective

To assess the effects of the study agent on subjects’ cognitive function.

Exploratory Objectives

- To identify specific biomarkers associated with cognitive functional changes and/or indicators of AD progression
- To assess the potential therapeutic effects of GRF6019 on AD biomarkers of neuronal death, synaptic function, inflammation, and growth factors utilizing the CSF collected in the optional CSF biomarker research.
- To identify potential indicators of AD progression and potential therapeutic effect based on brain imaging performed at the start and end of study for comparison.

1.2 Study Design

This is a prospective, randomized, double-blind, dose-comparison concurrent control study to assess the safety, tolerability, and feasibility of GRF6019, a [REDACTED] human plasma protein fraction, administered by intravenous (IV) infusion to subjects with mild to moderate AD, and will be conducted at up to 10 sites in the United States.

The overall duration of the study is approximately 15 months from study initiation (i.e., first subject enrolled) to study completion (i.e., last subject last visit). The recruitment period is expected to be approximately 12 months. The subject participation period is approximately 7 months from screening through end of study, unless prematurely discontinued.

The study consists of approximately 40 subjects randomized to one of the following two dose levels: 20 subjects at 100 mL and 20 subjects at 250 mL. All subjects will receive one infusion per day at the randomized dose for 5 consecutive days during weeks 1 and 13.

All subjects will undergo a screening visit, baseline visit, treatment visits, follow-up visits and an end of study/early termination visit. During the two 5-day dosing periods, subjects will reside in inpatient study observation units to facilitate safety evaluation. Subjects will be discharged from the inpatient facility the day after the 5th day of dosing. Subjects who are eligible and consent to participate in the optional cerebrospinal fluid (CSF) biomarker research at participating sites will undergo two lumbar punctures for CSF collection, the first occurring prior to initial dosing, and the second occurring following final dosing.

Safety and tolerability assessments will occur at every visit. Neurocognitive and psychomotor assessments will be performed at baseline and at periodic interim assessments following dosing. In the event of early termination of a subject, the end of study procedures will be performed unless the subject has withdrawn consent. A comprehensive efficacy and safety assessment of all data *in toto* will be conducted at the end of the study.

1.3 Sample Size Estimation

A total of approximately 40 subjects (20 in the 100 mL and 20 in the 250 mL groups) will be randomized in the study with the intent of obtaining ~30 evaluable subjects who have received at least 5 doses and completed through Visit 8. Subjects who discontinue prior to Visit 8 may be replaced. Subjects who withdraw or are withdrawn during screening will be replaced.

The primary endpoint of this study is safety and tolerability. Using the statistical approximation described by Hanley (aka the “Rule of Threes”), the upper bound of the 95% confidence interval for the rate of an unreported AE is at most 7.5% (3/number of subjects receiving active drug). In addition, the proposed sample size may be sufficient to identify trends in the effects of plasma-derived factors and in the relationship between dose and cognitive effects.

1.4 Randomization and Blinding

The study will be randomized with a mixed block size of 2 and 4 and stratified by sex. The randomization will be web-based and centralized. The randomization codes will be generated by a statistician who has no involvement in the study other than generation and maintenance of the randomization codes.

All study outcome measures will be assessed by blinded Outcomes Assessors. The Outcomes Assessors will observe the subject during the infusion of the study agent and collect and/or manage/report adverse events (AEs) and serious adverse events (SAEs). To ensure that Outcomes Assessors, subjects, and trial partners are unaware of the dose being administered, appropriate measures will be taken to mask the infusion pump and glass vials containing the study agent such that they will only be visible as necessary to the unblinded Infusion Nurse for appropriate dosing. In addition, a curtain, drape, or equivalent will be used to shield the infusion administration setup from view of all but the unblinded Infusion Nurse. Communication between the Outcomes Assessor and the Infusion Nurse will be restricted to only that required to ensure immediate patient safety.

Finally, to avoid potential unblinding based on patient albumin levels, serum albumin lab results will remain blinded until the conclusion of the study.

1.5 Study Data

The study data being analyzed per this Statistical Analysis Plan includes all clinical data captured by eCRF as well as safety lab data. The eCRF database will be locked for the final analyses and the final data transfers from the central lab will be utilized. Savonix Neurocognitive Assessments, Imaging data, and biomarker data, are not included in the eCRF database.

2 GENERAL ANALYSIS DEFINITIONS

All analysis dataset preparations and statistical analyses will be performed using SAS® version 9.4 or higher. No imputation will be performed for missing data unless stated otherwise. Listings for CSR Appendix 16.2 will include all the subject data points being collected or derived for analyses, and will be sorted by treatment group, site, and subject number.

[figure not shown]
2.1 Treatment Groups

The [REDACTED] treatment groups will be labelled as 100 mL, 250mL, [REDACTED] within the statistical output. [REDACTED]

2.2 Statistical Hypothesis Tests

Inasmuch as the study design is focused on safety and tolerability, the statistical approach taken with the secondary endpoints will be primarily descriptive with only modest amounts of hypothesis testing; within-subject changes from baseline for each dosing group and between-group differences will be evaluated for the purpose of designing future studies. Inferential statistics for any within-group and between-group comparisons will be described for each specific endpoint as applicable. For all statistical tests, the nominal two-sided p values will be reported.

2.3 Study Phase, Visit, and Day

The study is set up as shown above, along with assigned study period, visit, and day. In general, the baseline is defined as the last assessment before the first intake of the study medication unless otherwise specified. All scheduled assessments after first administration of study drug will be used.

Repeat/unscheduled assessments will not be used in descriptive statistics or any per-time point analyses but will be shown in listings as applicable. Pre-dose unscheduled assessments will be taken into account for baseline determination and post first dose unscheduled assessments will be taken into account for worst-case determination as applicable.

Reference date refers to the start date of the first study drug administration. All efficacy and safety assessments at all visits will be assigned a day relative to this date. The relative day will be defined as: visit date – reference date + 1 for visits on or after the reference date and visit date – reference date for visits before the reference date. Consequently, there is no 'Day 0' defined.

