Nonclinical studies conducted at Alkahest evaluated the effects of both young plasma and plasma protein fraction using various dosing paradigms in NODscid, NSG (NODscid Gamma) and C57BL/6J mice. Initially, mice were dosed with 150 μ L of [REDACTED] plasma, [REDACTED] plasma protein fraction or saline (control) via IV infusions 2 times per week for 5 weeks ([REDACTED]). A subsequent study examined the same dosing regimen for a period of 23 weeks, to assess the effects of treatment on age-dependent changes in behavioral and cognitive function over a period of approximately 6 months ([REDACTED]). Following these early studies, a novel dosing regimen of 150 μ L for 7 consecutive days (referred to as "pulsed dosing") was evaluated both alone and compared to other intermittent weekly dosing regimens ([REDACTED]). A final study examined pulsed dosing of 150 μ L for 5 consecutive days ([REDACTED]), which is the pulsed dosing regimen chosen for ALK6019-201.

Based on these nonclinical studies, significant improvements in cognitive performance and histological correlates were observed with a [REDACTED] plasma protein fraction. In addition, studies with [REDACTED] plasma demonstrated that the beneficial effect was observed long after initial dosing, indicating there is not a requirement for continuous repeat dosing. The effects were long-lived but did diminish over time such that 3 months after dosing benefits just reached significance.

Together, these studies indicate that 5 consecutive days of dosing ("pulsed dosing") of GRF6019, a batch of [REDACTED]

[REDACTED]. If safety and efficacy are demonstrated with GRF6019, pulsed dosing may be more convenient than weekly or monthly dosing for patients.

A prospective, randomized, double-blind, dose-comparison concurrent control study design has been selected to reduce or eliminate bias while facilitating the identification of a safe and feasible dosing paradigm, trends in changes of neurocognitive endpoints, and potential plasma derived factors that may affect these parameters. Within-patient and between-group cognitive changes associated with the 2 dose levels of GRF6019 will be evaluated.

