7.3.2 BASELINE

Visit 2, Baseline (Days -7 to -1)

- Re-review screening assessments for eligibility (e.g., MMSE scores, lab values)
- Review AEs and concomitant medications
- Collect the following:
 - Vital signs
 - Samples for proteomics/epigenetics/biobanking (fasting samples are preferred)
 - Buccal swab for ApoE Genotype testing
- Ensure the subject has had an opportunity to eat a meal prior to commencing cognitive and motor testing
- Perform cognitive and motor testing in the following order unless otherwise specified:
 1. Savonix Full Battery
 2. ADAS-Cog/11
 3. Grooved Pegboard

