7.3.4 TREATMENT

There are two inpatient treatment periods scheduled during the trial, each with a total of 5 infusions. It is anticipated that sites will infuse subjects with 5 doses over 5 days. A “grace day” is allowed in the event of unanticipated safety or health concerns during each inpatient treatment period.

Visits 3-7 (Days 1-5) and 11-15 (Days 85*-89):

*Day 85 has a ± 7-day window. Visits 12-16 should follow consecutively.

- Perform the following procedures prior to administering study treatment:
 - Review AEs and concomitant medications
 - Obtain blood and urine samples for comprehensive laboratory panel; fasting samples preferred **(Visits 4, 6, 12, and 14 Only)**
 - Obtain samples for proteomics/epigenetics/biobanking; fasting samples preferred **(Visits 3 and 11 Only)**
 - Obtain i-STAT safety laboratory test samples and assess results before each infusion
 - Perform targeted physical exam (i.e. auscultation of heart and lungs and assessment of peripheral edema)
 - Measure and record the subject’s weight in kilograms
 - Perform 12-lead ECG **(Visit 11 Only)**
 - Ensure the subject has had an opportunity to eat a meal prior to cognitive and motor testing
 - Administer the Savonix Brief Battery
 - Perform ADAS-Cog/11 **(Visit 11 Only)**
 - Collect pre-infusion vital signs
- Administer study treatment and perform safety assessments per the Infusion Administration Manual
- Post-infusion: perform 12-lead ECG **(Visits 7 and 15 Only)**

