5.2 Alzheimer's Disease Assessment Scale-Cognitive Subscale (ADAS Cog/11)

The ADAS-Cog/11 (Rosen 1984) includes 11 items assessing cognitive function:

- Word Recall: the mean of the three trials is used, rounded to 2 decimal places
- Command
- Constructional Praxis
- Naming Objects and Fingers
- Ideational Praxis
- Orientation
- Word Recognition
- Remembering Test Instructions
- Comprehension
- Word Finding Difficulty
- Spoken Language Ability

Although available in the raw data, the ADAS-Cog/11 total score is derived as a linear sum of the scores recorded for the 11 individual domains. Higher scores reflect greater cognitive impairment.

Changes from baseline for the total score as well as 11 individual domain scores and will be summarized at each scheduled timepoint (Days 28, 112, and 168) (Table 14.2.2).

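### ADAS-Cog/11 is measured just before the second course, but the SAP tabulates neither that score nor any change from it, and the ADAS-Cog and Pegboard day lists look swapped

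*SAP*

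**What the plan says.** **Reference value.** SAP 2.3 states: "In general, the baseline is defined as the last assessment before the first intake of the study medication unless otherwise specified". For ADAS-Cog/11 that is the Visit 2 score (Days -7 to -1).

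**ADAS-Cog summaries.** SAP 5.2 states: "Changes from baseline for the total score as well as 11 individual domain scores and will be summarized at each scheduled timepoint". It then names Days 28, 112 and 168 (Table 14.2.2) and gives no other reference value.

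**Collection.** Protocol 7.3.4 opens its list for infusion days with "Perform the following procedures prior to administering study treatment". The list includes "Perform ADAS-Cog/11", marked for Visit 11 alone. Protocol 7.3.5 and 7.3.6 and the Schedule of Events (Section 17) add Days 6, 28, 90, 112 and 168. Of the eight scales in SAP 5.1-5.8, only ADAS-Cog/11 is scheduled immediately before the second course.

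**Pegboard summaries.** SAP 5.3 lists Days 6, 28, 85, 90, 112 and 168, although the protocol schedules that test after baseline only on Days 28, 112 and 168.

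**Purpose.** SAP 2.2 says that within-subject changes by dose and between-group differences are evaluated to help design later studies.

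**The concern.** A score taken just before re-dosing lets a reader see where subjects stood when the second course began and how they moved afterwards. The second course is also the trial's only within-subject repeat of the pulse. Under SAP 5.2 as written, the Day 85 score appears in no summary table, and no change is measured from it. The Day 112 change that is tabulated runs from before the first infusion, so within a dose group it mixes three things: whatever remains of course 1, about 12 weeks of Alzheimer's disease course, and course 2.

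What is at stake is usable descriptive information for planning later trials. No stated conclusion becomes invalid. Separately, the SAP 5.3 list asks the programmers for Pegboard summaries at three visits where the test is not done.

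**Working it through.** **1. Day lists side by side**

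| Scale | Protocol, after baseline | SAP |
|---|---|---|
| ADAS-Cog/11 | Days 6, 28, 85, 90, 112, 168 | 5.2: Days 28, 112, 168 |
| Grooved Pegboard | Days 28, 112, 168 | 5.3: Days 6, 28, 85, 90, 112, 168 |

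Each SAP list matches the protocol's schedule for the other test exactly. SAP 5.2 also conflicts with SAP 2.3 and 2.6, which call for every scheduled post-dose assessment to be used and every planned timepoint to be shown.

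**2. The plan's own timing.** Infusion 1 is on Day 1 and infusion 6 on Day 85: 85 - 1 = 84 days = 12.0 weeks, consistent with Week 13. With the ±7-day window it is 77-91 days.

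**3. Interval from baseline.** There is no Day 0, so Day -k to Day d is d + k - 1 days.
- Baseline to Day 85: 85 + 1 - 1 = 85 to 85 + 7 - 1 = 91 days. With the Visit 11 window: 78 to 98 days.
- Baseline to Day 112: 112 to 118 days. Share before infusion 6: 85/112 = 76% to 91/118 = 77%.
- Baseline to Day 168: 168 to 174 days. Share: 85/168 = 51% to 91/174 = 52%.
- Baseline to Day 90, if the list is corrected: 90 to 96 days. Share: 85/90 = 94% to 91/96 = 95%.

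From Day 85, the nominal intervals are 5 days to Day 90 and 27 days to Day 112.

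**4. Size of the disease-course part.** The documents give no rate of decline. Assume 2 to 8 ADAS-Cog points per year, for illustration only; drift = rate × days / 365.25.
- Over 84 days: 2 × 84/365.25 = 0.46 to 8 × 84/365.25 = 1.84 points.
- Over 27 days: 2 × 27/365.25 = 0.15 to 8 × 27/365.25 = 0.59 points.

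**5. Would correcting the lists be enough?** It would put Day 85 in Table 14.2.2, but still as a change from baseline. Where the same subjects contribute, subtracting means gives the average course-2 change. Its SD does not follow: SD² = s85² + s112² - 2·r·s85·s112, and the correlation r is not planned output. The pairing exists only in Listing 16.2.6.2.

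**6. Who contributes.** The Evaluable set needs 5 of 10 doses (SAP 2.4), so the Day 112 and Day 168 summaries may include subjects with no course-2 infusion. The plan's figure of about 30 evaluable reproduces (40 × 0.75 = 30), but Protocol 10.5 ties it to completion of Visit 8, before course 2. The documents therefore give no expected number of subjects with both Day 85 and Day 90 scores.

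**7. Comparability of the courses.** Windows are counted from Visit 3 (Protocol 7.3). Visit 11 falls on Days 78-92 and Visit 17 on Days 105-119, so the gap can be 105 - 92 = 13 to 119 - 78 = 41 days. Baseline to Visit 9 (Days 21-35) is 21 to 41 days. Baseline to Day 6 is 6 to 12 days, against 5 days for Day 85 to Day 90 (6 with a grace day in that course).

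**The case against.** The case for leaving the plan alone is substantial. No objective or endpoint names a separate second-course effect. The cognitive endpoints are defined as changes from baseline, the tests are optional, there is no multiplicity adjustment, and both documents disclaim power. Individual ADAS-Cog scores are listed, so the change can still be derived. All of that stands, and it limits the point to a minor one.

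Three stronger readings are tempting, and the documents do not support them.

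- *Disease course distorts the dose comparison.* Decline common to both randomized doses cancels in expectation. A lasting course-1 dose difference does not cancel, but it belongs to the effect of the assigned dose, which change from baseline is meant to capture.
- *Without a Day 85 reference the trial cannot say whether the second pulse moved cognition.* With it, the trial could not establish that either. Both arms receive active drug, and Day 90 minus Day 85 is a short retest within an inpatient stay. The rationale also cuts both ways: "The effects were long-lived but did diminish over time such that 3 months after dosing benefits just reached significance". That is nonclinical evidence of fading, but also of benefit still detectable at about the time of re-dosing, so carry-over at Day 85 is plausible.
- *The new reference should drive a dose test or a pooled estimate.* An ANCOVA adjusted for Day 85 would condition on a score that dose may already have changed, in subjects selected for reaching course 2. Averaging the two course changes would treat unequal windows as matched, and any precision gain would rest on SDs and correlations that the documents do not give.

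What survives is that a scheduled measurement is left out of the tables, apparently through exchanged day lists, and that a simple paired summary of it is not planned. SAP 6.3 already re-references vital signs to each infusion day's pre-dose value, so a second reference has a precedent in this SAP.

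**Conclusion.** The point holds as a minor one. The text establishes that there is one pre-first-dose reference, that an ADAS-Cog/11 score is scheduled before infusion 6, that no change from that score is planned, and that the day lists in SAP 5.2 and 5.3 fit each other's test. The share of the Day 112 interval that precedes infusion 6 (76-77%) follows from nominal visit days. The drift of 0.46 to 1.84 points over 84 days rests on an assumed 2 to 8 points per year and is only illustrative.

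The limitation concerns how the within-dose changes are read. It does not bias the randomized dose comparison, affect the primary safety endpoints or change the sample size.

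**What to change.** 1. **Correct the day lists.** SAP 5.2 (Table 14.2.2): ADAS-Cog/11 at Days 6, 28, 85, 90, 112 and 168. SAP 5.3 (Table 14.2.3): Grooved Pegboard at Days 28, 112 and 168.
2. **Keep change from baseline as the main summary and add a supplementary descriptive panel** for the ADAS-Cog/11 total score: Day 90 minus Day 85 and Day 112 minus Day 85, by dose, with n, mean, SD and 95% CI. Include subjects with a Visit 11 score and at least one course-2 infusion. Show it beside the Day 6 and Day 28 changes from baseline.
3. **State its limits in the SAP.** The panel is within-dose and uncontrolled, it includes retest, inpatient-setting and carry-over effects, and it covers only subjects who reached course 2. Attach no between-dose test to it and do not average the courses.

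The cost is two corrected lists, one SAP paragraph and one table panel, with no new data. The downside is a few more nominal descriptive estimates. To count as pre-specified, it should be in the SAP before database lock and unblinding.
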